4.4 Sample size calculation

The total number of patients included in this pilot study will be 6-10 patients. The main objective of the current study is to determine feasibility of combining EBRT and MR-HIFU within a 3 hour - 4 day time window. As this is a first-in-man study there is no data present to perform a formal sample size calculation. We will closely monitor unexpected side effects. Changes in the protocol will be made where appropriate.

5. TREATMENT OF SUBJECTS

5.1 Investigational product/treatment

The intervention that will be studied is single or multiple fraction EBRT in combination with MR-HIFU within a 3 hour - 4 day time window. The combined treatment is aimed at rapid and persistent relief of metastatic bone pain. For more information on the Sonalieve MR-HIFU Bone metastases Therapy System we refer to the Investigator's brochure.

5.2 Use of co-intervention

5.2.1 EBRT

In a first step, patients will undergo EBRT according to the standard of care on a priority base within maximally 7 days after they visit the outpatient clinic of the Department of Radiation Oncology. Patients undergo a planning CT scan, as part of standard care, in treatment position.

EBRT is provided as single fraction radiotherapy or multiple fraction radiotherapy. According to the American Society for Radiation Oncology (2012) evidence-based guidelines for the management of bone metastases, a single fraction of 8 Gray (Gy) has an equivalent pain relief quality indicator compared to longer courses of radiotherapy, including 5 or 6 fractions of 4 Gy and 10 fractions of 3 Gy (Lutz et al, 2014). However, multiple fraction radiotherapy may have a larger contribution to local tumor control and is therefore often used in patients with a longer life expectancy. The above dose fractionation schemes are recommended as quality indicators of palliative radiotherapy by the American National Quality Measures for EBRT for bone metastases. Acute and late side effects of radiotherapy for bone metastases are generally similar with single fraction versus multi fraction regimens, with some studies showing decreased acute side effects in patients receiving single-fraction radiotherapy. Time to pain relief also appears similar, with an optimal time to measure pain relief of 2 months after the completion of palliative radiotherapy.

5.2.2 Pain medication

Subjects should receive pain medication if and as required by their symptoms, both before and after the combined EBRT and MR-HIFU treatment. The amount of pain medication used is part of the secondary endpoints of the study, and should be recorded at baseline before treatment and during the follow-up after treatment.

Pain medication used for treatment-related pain shall be noted in a separate Data Element in the CRF and in Concomitant Medication Forms. The fact that the medication was used for

treatment related pain is marked on the Concomitant Medication Forms, and the use of this medication will not be considered in the assessment of the pain response.

Patients can continue to use chemotherapy, targeted therapies (e.g. angiogenesis inhibitors) or bisphosphonates if they are already using them. The treatment type and the date the treatment was started/stopped will be recorded.

During the MR-HIFU treatment the patient will be under conscious sedation. This will enable adequate pain control and ensure a stable patient position during treatment. The sedatives used are at the preference of the anaesthesiologist/sedation specialist.

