7.2 Randomisation, blinding and treatment allocation

This study is a non-randomized pilot study. All eligible subjects will first receive EBRT followed by MR-HIFU. As such, there will be no blinding of the study participants and their doctors.

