9. STATISTICAL ANALYSIS

In order to reach the objectives, a two stage approach will be used following the IDEAL recommendations: IDEAL stage 1, i.e. innovation/proof of concept of EBRT followed by MR-HIFU within a 3 hours - 4 days time window, followed by IDEAL stage 2a, i.e. development of the new treatment strategy.

In the first stage, we will include three patients in whom the combined treatment will be applied and tested for the first time. In this stage, the main objective is to demonstrate the feasibility of the combined treatment strategy and describe it in detail. The report will contain clear anonymous details of the patient, exact description of the primary tumor, site of metastases, extent of the index lesion, rationale for the use of this procedure in these particular patients and a very detailed description of technical and clinical aspects of the procedures. For all patients, technical success, detailed pain scores (baseline and follow up), neurological symptoms (baseline and follow up), complications, toxicity, use of analgesics, and other relevant outcomes will be reported on an individual level. The patients reported experience will also be used to make adjustments to the logistics and treatment protocol.

After stage 1, an interval of at least two weeks will be implemented before treating the next patient to allow identification of early major problems.

Progression to stage 2a (Development) will be justified after we have demonstrated feasibility of the combined procedure, without major technical problems or safety issues. In stage 2a, the main focus is safety and technical feasibility of the combined procedure, which will be measured in 3-7 consecutive patients meeting the inclusion criteria and none of the exclusion criteria.

For all patients, we will report toxicity and pain response. The patient-reported worst pain will be used. This is consistent with the latest version of the International Consensus for clinical trial endpoints on bone pain palliation with radiotherapy.

Pain responders are defined as patients with:

1. Pain score (numerical rating scale; NRS) at the treated site of zero without analgesic increase (complete response);
2. Reduction of pain score of at least 2 points at the treated site without analgesic increase (partial response);
3. Analgesic reduction of 25% or more without increase in pain (partial response).

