10.3 Benefits and risks assessment, group relatedness

The PRE-FURTHER study is designed to assess the feasibility of the combined EBRT MR-HIFU treatment of painful bone metastases.

EBRT is the current standard of care. The most common adverse event of EBRT is a temporal increase of the pain after the treatment also known as pain flare (Mavrogenis, 2016). 'Pain flare' is observed in 2 to 44 percent of patients and can have an important impact on quality of life.

Pathologic fractures of weight-bearing bones occur in 10-20% of patients with bone metastases, with femoral metastases accounting for the largest part of these fractures (Body, 1992; Eastley, 2012) The risk of pathological fractures after radiotherapy has been well documented. In the most recent systematic review of palliative radiotherapy trials for bone metastases, comparing single versus multiple fraction regimens, one of the secondary outcomes was pathological fracture rate after radiotherapy (Chow, 2007). Several studies reported data for pathological fracture rates (Bone Pain Trial Working Party, 1999; Cole, 1989; Hartsell, 2005; Kaasa, 2006, Nielsen, 1998; Price, 1986; Roos, 2005). The pooled pathological fracture rates ranged from 2.8% to 3.2% with no significant differences for treatment schedules. Most of these studies excluded patients with (impending) pathological fractures, which is also the case in this pilot study.

However, EBRT is only effective in part of the patients and it may take several weeks before pain reduction is achieved. The additional MR-HIFU treatment is expected to lead to a more rapid pain relief and may even prevent or reduce the pain flare. Besides occasional minor thermal skin burns, no serious adverse effects are expected as a result of the additional MR-HIFU treatment. A detailed summary of the results of the complete risk analysis performed by the Supplier is given in the Investigator's Brochure (chapter 10 and appendix 1).

The Investigator's Brochure summarizes the outcomes and reported adverse events of previous key MR-HIFU studies. The benefits and positive outcomes reported in these previous studies have been weighed against the identified risks. This weighing has led to CE labeling of the device in Europe.

In addition to those procedure- or device-related adverse events the following adverse events are anticipated in this patient population, but expected to be unrelated to the combined treatment procedure:

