12.2 Synthesis

MR-HIFU ablation is a powerful technique that can rapidly increase the temperature in tissues to lethal temperatures. This makes it an useful tool for the treatment of a whole array of diseases. However, MR-HIFU can also potentially induce thermal damage to vital tissues and organs. For this reason, clinical studies focus on real-time treatment monitoring and optimizing the accuracy and precision of the ablation process. Previous MR-HIFU studies for painful bone metastases demonstrated that MR-HIFU is sufficiently safe and effective. The MR-HIFU procedures are performed under MRI guidance which means that the treated tissue is visualized during the entire treatment and that the temperature of the targeted region is continuously depicted in temperature maps.

In the presented literature, minor adverse events occurred in some patients and mainly consisted of mild skin burns and mild pain. No severe adverse events were reported. All minor adverse events subsided within a maximum of 10 days and had no sequelae.

The use of PSA for the MR-HIFU treatment has two major advantages over using local or no anesthesia. First, patients are able to lie still during the entire treatment, which decreases the risk of side effects and impaired treatment efficacy due to patient motion. Second, subjects experience less discomfort and pain during MR-HIFU treatment. The risks of the sedation used are very low.

We cannot fully exclude unexpected complications and (serious) adverse events due to the combination of EBRT and MR-HIFU. However, the minimal interval of 3 hours between the EBRT and MR-HIFU treatment was chosen in such a way that a detrimental interaction between the two treatments is not to be expected. Moreover, their mechanism of action differs and both treatments have proven to be safe when applied alone. Therefore, we do not expect any SAE.

Overall, it is deemed that the potential benefits of this study, both to the individual patient, as manifested by potential rapid and long lasting pain relief at the treated lesion, and in the end to the wider patient community, as manifested by potential wider availability of an additional non-invasive option for pain palliation in bone metastases, outweighs the potential risks.

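### Pain response is scored net of analgesics marked as treatment-related, so a patient whose total use rose can count as a responder; section 9 should also report response with all analgesics counted

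*Combined protocol and SAP*

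**What the plan says.** Section 5.2.2 has medication for treatment-related pain recorded apart from the rest: "Pain medication used for treatment-related pain shall be noted in a separate Data Element in the CRF". It is also marked on the concomitant medication forms. The section then states how the mark is used: "the use of this medication will not be considered in the assessment of the pain response".

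Section 9 defines three ways to be a pain responder, using worst pain on the numeric rating scale (NRS):

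- complete response, a score "at the treated site of zero without analgesic increase (complete response");
- partial response by pain, "Reduction of pain score of at least 2 points at the treated site without analgesic increase (partial response");
- partial response by medication, "Analgesic reduction of 25% or more without increase in pain (partial response").

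Section 9 does not refer to 5.2.2 and plans a single classification. It also says that medication before and after the procedure is documented, with opioids as a daily oral morphine equivalent, and that results are descriptive with no tests.

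The amount of analgesic used is itself part of the secondary endpoints (5.2.2). Baseline use is taken as the total over the preceding 24 hours, after written consent (7.3). On blinding, section 7.2 says "there will be no blinding of the study participants and their doctors".

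**The concern.** The condition that analgesics did not rise stops a fall in pain from being credited to the treatment when extra medication produced it. The exclusion in 5.2.2 lifts that safeguard for one class of medication. A patient can take more analgesic in total, report less pain partly for that reason, and still satisfy the criterion.

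The class rests on a judgement. The documents do not define treatment-related pain for this purpose, limit how long after treatment the mark may be used, or say who decides. Patients and doctors know what was given, and two sites apply the rule.

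At stake is the descriptive response figure at each call. Rapidity of pain relief is a secondary objective (2.2) and rests on the earliest calls. Section 12.2 says of minor adverse events in the earlier MR-HIFU literature, which included mild pain: "All minor adverse events subsided within a maximum of 10 days and had no sequelae". Two of the five planned calls, days 3 and 7, fall within 10 days of MR-HIFU. If the mark covers pain after the procedure, those are the calls where the exclusion is most likely to act.

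**Working it through.** The documents give no response rate or reclassification rate to reproduce. The check applies the section 9 criteria to net and to total analgesic use.

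**Inputs from the documents.** Criteria: section 9. Exclusion: 5.2.2. Number of patients: 6 to 10 (4.4). Baseline measure: total use (7.3).

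**Direction.** Let B be baseline use with no marked medication, U unmarked use at the call, and M marked use at the call, M ≥ 0. Total use at the call is T = U + M, so U ≤ T.

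- No increase: T ≤ B implies U ≤ B.
- Reduction of at least 25%: T ≤ 0.75B implies U ≤ 0.75B.

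Every responder on total use is then also a responder on net use, but not the reverse. With such a baseline the exclusion can only keep or raise the count.

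**Illustrations.** Pain scores and doses are assumed; doses are mg oral morphine equivalent per day.

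| Patient | Worst NRS | Baseline | At the call | Net change | Total change | Net result | Total result |
|---|---|---|---|---|---|---|---|
| A | 7 to 0 | 60 | 60 + 30 marked | 60/60 − 1 = 0% | 90/60 − 1 = +50% | complete response | non-response |
| B | 7 to 5 | 60 | 60 + 30 marked | 60/60 − 1 = 0% | 90/60 − 1 = +50% | partial response | non-response |
| C | 7 to 7 | 60 | 45 + 30 marked | 45/60 − 1 = −25% | 75/60 − 1 = +25% | partial response | non-response |
| D | 7 to 7 | 60 + 30 marked | 65 | 65/60 − 1 = +8.3% | 65/90 − 1 = −27.8% | non-response | partial response |

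Patients A to C show that each of the three routes can be met while total use rises.

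Patient D shows the opposite direction, with the exclusion applied at baseline as well. This is possible because of the sequence in 7.3. Single-fraction radiotherapy is usually given on the day of the first visit, oral consent is sought by phone at least a day later, and baseline analgesics are collected after written consent. Section 5.2.2 places baseline before treatment, but this sequence allows it to follow radiotherapy.

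**Size per patient.** One patient changing category moves the response rate by 1/10 = 10.0 points (10 patients) or 1/6 = 16.7 points (6 patients).

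**The case against.** The strongest reply is that nothing is undecided. Section 5.2.2 says marked medication is left out of the pain response, and pain response is what section 9 defines. That stands. A reader might infer from the silence of section 9 that the protocol wavers between total and net use; the documents do not support this. The rule is net and pre-specified, and leaving out procedural analgesia is defensible.

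Second, much is already reported. Section 9 promises analgesic use for individual patients, and medication is documented before and after the procedure. This stands in part. The individual-level promise is in the stage 1 paragraph, which covers three patients. The stage 2a text promises toxicity and pain response. Documented medication is also not the same as a response figure with all analgesics counted.

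Third, the mark may be narrower than it looks. Section 7.3 mentions recording medication for treatment-related pain directly after describing sedation and analgesia for MR-HIFU. If only peri-procedural analgesia is meant, little may be excluded by day 3. This is a fair reading and would shrink the effect, but no text confines the mark to that period.

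Fourth, a shift of 10.0 to 16.7 points for one patient holds for any binary endpoint in a series this small. That is true: the figure scales the effect and is not evidence that it will occur.

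**Conclusion.** The point holds as a minor reporting matter. The existing rule lets a patient with higher total analgesic use be counted as a responder, on a mark that is undefined and set without blinding, and no planned response figure shows the result with all analgesics counted. Each affected patient moves the response rate by 10.0 to 16.7 points. How many would be affected cannot be said from the documents.

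Two stronger readings should be resisted. A reader might infer that the exclusion always favours the treatment. It does so only when baseline holds no marked medication; patient D shows the reverse. A reader might also take the range for pain flare after radiotherapy in 10.3, which "is observed in 2 to 44 percent of patients", as the rate of reclassification or its upper limit. It is neither. The protocol does not say that flare medication is marked, and the range leaves out pain from MR-HIFU. A patient in flare is also less likely to meet a pain criterion, and 10.3 expects that MR-HIFU may reduce flare.

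The response endpoint is secondary, descriptive and untested, so neither the design nor the primary feasibility outcome is affected.

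**What to change.** In section 9, cite 5.2.2 and report pain response at each follow-up call (about days 3, 7, 14, 21 and 28), for all patients in stages 1 and 2a, in two versions:

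1. marked analgesics excluded, the existing rule, kept as it is;
2. all analgesics counted.

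Within each version, treat baseline and follow-up use the same way: leave marked medication out of both, or count it in both. The separate CRF data element already planned supplies what is needed. Optionally, add one line to 5.2.2 in which the sponsor states when the mark is set and for how long it may apply.

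No new data, patients or calls are required. The text change would be notified to the ethics committee as an amendment (11.3). The price is two response figures per call, and a patient on short-term procedural analgesia may be a non-responder in one of them, which the report should explain. The change concerns measurement and reporting only, not which analgesics patients receive.

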6. INVESTIGATIONAL PRODUCT

6.1 Name and description of investigational product

The Profound MR-HIFU Sonalleve System integrates a high intensity phased array focused ultrasound transducer with a magnetic resonance (MR) imaging system and electromechanical transducer positioning system to deliver spatially and temporally controlled ultrasound energy and thermal heat to tissues non-invasively. The MR system is used to provide images to plan the therapy, and to guide and monitor the thermal ablation with thermal imaging during the treatment.

The MR-HIFU system consists of:

- HIFU Therapy Console, where treatment planning, treatment control and post-treatment operations are performed;
- Generator Cabinet that houses the control electronics and the 256-channel ultrasound generator with individually programmable amplitude and phase;
- Patient Tabletop that houses the electromechanical transducer positioning system, the phased array 256-channel ultrasound transducer immersed in a liquid bath, and integrated radiofrequency surface and wrap-around coils for MR imaging.

Patient contact materials are described in the Investigator's Brochure. The users are required to be trained for safety, system/treatment workflow and quality assurance (QA) procedures.

The Profound Sonalleve MR-HIFU system used in Isala and UMC Utrecht is a CE-marked device for pain palliation of bone metastases. They were manufactured by Philips Medical Systems Oy, Vantaa, Finland. The systems will be traceable by their serial number and the Device History Records maintained by the manufacturer. One Sonalleve MR-HIFU device is available at each study location.

Traditionally, the Profound Sonalleve MR-HIFU device allows physicians to heat and ablate tissue under MR image guidance. Bone metastases cause bone destabilization (due to destruction) leading to stimulation of the mechanosensitive receptors in the periosteum (outer bone covering). HIFU treatment will aim at ablating the periosteum and thus reducing the localized bone pain. Ablation can be performed with volumetric techniques, which are designed to allow heating of larger zones or cells in one sonication. During a sonication, the transducer applies heat in a continuous manner to adjacent points within the treatment cell. In the bone HIFU treatment, the treatment cells

are placed within a target treatment area to sonicate the targeted bone. Full treatment is performed by stepping through several treatment cells with cooling times between each sonication. Each HIFU ablation is performed with user selected ultrasound power set to achieve sufficient tissue heating to ablate the periosteal nerves, typically achieved in the temperature range 55-70°C. Heating of the surrounding tissue can be monitored by MR temperature mapping. The duration of the exposures linked with the cell size are fixed by the system.

Three different ablation approaches will be used to ablate the periosteum, i.e., the near-field approach, the direct approach and the soft-tissue approach. The main factors determining choice of ablation approach are the presence of cortical destruction, tissue in the far field and safety concerns. In patients with an intact cortex at metastasis level ablation of the metastasis is not possible. In that case the periost is ablated by heating the cortex. In patients with a (partly) destructed cortex it is unclear which part of the periost is still intact. The tumor itself and the overlying periost will be ablated. All three approaches aim for pain reduction.

The Profound Sonalleve MR-HIFU system displays real-time temperature data overlaid on anatomical MR images, accumulated thermal dose information, and the ultrasound therapy parameters such as transmitted output power, frequency, and timing. Additionally, the operator can select specific thermal areas to obtain temperature readouts. The temperature display is updated every 3 seconds with new information.

For more details about the system, please refer to the Investigator's Brochure.

6.2 Summary of findings from non-clinical studies

See Investigator's brochure for the summary of findings from non-clinical MR-HIFU studies (pages 17 - 24).

6.3 Summary of findings from clinical studies

See chapter 1.3 and Investigator's brochure for the summary of findings from clinical MR-HIFU studies (pages 25 - 30).

6.4 Summary of known and potential risks and benefits

The Profound Sonalleve MRI-HIFU system is able to elevate temperatures at the bone interfaces, inside the bone and inside the bone metastasis with fast acquisition of thermal maps covering a large volume (including the skin), and with continuous heating of adjacent points, which reduces the amount of energy deposited. The device provides the user with

sufficient information about the location of temperature elevation, volume of the ablation, and the temperature and thermal dose behavior of the heated tissue. With the device the temperature of the bone surface can be elevated and a part of the soft tissue ablated to the extent that provides a significant improvement to the symptoms experienced by the patient.

The risks are HIFU physics and clinical practice dependent rather than specific HIFU device dependent. The highest risk is unintended heating of tissue causing burns.

The Sonalleve device is equipped with several safety measures to reduce the risks.

The system offers e.g. real-time feedback to inform the operator of various safety parameters. The user can monitor for:

- Undesired temperature elevations in off-focal and focal areas.
- A significant drop in transmitted power.
- A significant drop in temperature versus time curve at the focus

The ultrasound system will automatically shut down if:

- The transducer heats to critical temperatures.
- The measured output power is higher or substantially lower than the requested power.
- High levels of reflected/backscattered power are detected in the amplifiers.
- Any system control element fails to respond correctly to a control request.

The sonication can also be shut down manually by the Patient Emergency Stop Button, the operator controlled Safety Device, or the stop button in the User Interface. A sonication shut down is indicated both by the user interface and by an indicator light on the operator console. A manual reset or other action by the operator is required to continue use of the system after a safety shutdown or use of the stop button by a patient.

The duration of the treatment is dependent on the area which needs to be ablated. In general, it takes one to two hours to treat the average patient with one or more painful bone metastases. Since EBRT only takes up to 20 minutes and there is no need for sedation, patients could experience the MR-HIFU treatment as more cumbersome. Based on the results from previous studies we have valid reason to tell our patients that, even though MR-HIFU is more cumbersome, it is expected to lead to much faster pain relief and perhaps even longer lasting pain relief in the majority of patients.

